#### **9.1.8 Administration**

Administer the infusion over 60 minutes (+/- 10 minutes) through an intravenous line containing a sterile, non-pyrogenic, low protein binding in-line filter (pore size of 0.2 micrometer to 1.2 micrometer).

#### **9.1.9 Ordering**

Each institution will order nivolumab directly from the supplier Bristol Myers Squibb Pharmaceuticals (BMS). A study specific order form will be supplied by the lead site.

#### **9.1.10 Accountability**

The investigator, or a responsible party designated by the investigator, should maintain a careful record of the inventory and disposition of the agent using the NCI Drug Accountability Record Form (DARF) or another comparable drug accountability form. (See the NCI Investigator's Handbook for Procedures for Drug Accountability and Storage.)

#### **9.1.11 Destruction and Return**

For this study, study drugs (those supplied by BMS or sourced by the investigator) such as partially used study drug containers, vials and syringes may be destroyed on site.

On-site destruction is allowed provided the following minimal standards are met:

- On-site disposal practices must not expose humans to risks from the drug.
- On-site disposal practices and procedures are in agreement with applicable laws and regulations, including any special requirements for controlled or hazardous substances. BMS will be notified of all Nivolumab drug destructions.
- Written procedures for on-site disposal are available and followed. The procedures must be filed with the site's SOPs and a copy provided to BMS upon request.
- Records are maintained that allow for traceability of each container, including the date disposed of, quantity disposed, and identification (ID) of the person disposing the containers. The method of disposal, (e.g., incinerator, licensed sanitary landfill, or licensed waste disposal vendor) must be documented.

### **9.2 DC/MM Fusion Vaccine**

#### **9.2.1 Isolation of Tumor Cells**

Patients will undergo aspiration of 30 mL of bone marrow from which myeloma cell preparations will be generated. Bone marrow will be aspirated into sterile heparinized syringes with approximately 5-8 mL aspirated per syringe to avoid significant hemodilution of bone marrow mononuclear cells. Bone marrow aspirate samples will be transferred in sterile syringes to the cell manipulation facility, and mononuclear cells will be isolated by ficoll density gradient centrifugation. Autologous plasma will be obtained by harvesting supernatant following centrifugation of 50 mL of peripheral blood. Bone marrow mononuclear cells will be cultured in media with 10% autologous plasma. An aliquot of the tumor cells will undergo immunohistochemical staining as detailed below. Tumor lysate will be prepared by freeze/thawing or sonication of an aliquot of tumor cells for immunological analysis. Myeloma cells may be frozen in 10% DMSO/90% autologous plasma stored in liquid nitrogen for potential subsequent vaccine generation.

#### **9.2.2 DC Generation**

Patients will undergo leukapheresis for DC and vaccine generation. The leukapheresis product will be transferred in a sterile container to the cell manipulation facility, and PBMC will be isolated from the leukapheresis product and cultured in the presence of autologous plasma for 1- 2 hours and then cultured for 5-7 days with GM-CSF and IL-4. Cultures are re-fed with cytokines after 3 days. Twenty-five ng/mL of TNF $\alpha$  will be then be added for 48-72 hours to induce DC maturation. An aliquot of the DC preparation will undergo immunocytochemical staining for immunophenotypic analysis.

#### **9.2.3 DC/MM Fusion Vaccine Preparation**

Tumor cells will be thawed (when relevant). Tumor cells and DC preparations will be co-cultured at ratio of 1:3 and washed in serum-free medium. After low-speed centrifugation, the cell pellet will be re-suspended in 50% solution of polyethylene glycol (PEG) and will be progressively diluted by the slow addition of serum-free medium. An aliquot of the DC, tumor, and fusion cell preparations will undergo immunocytochemical analysis for vaccine characterization. Dependent on cell yields, 3 doses of  $1-5 \times 10^6$  fusion cells will be prepared. The fusion cells will then be separated into appropriate aliquots of fusion cells, radiated at 30 Gy, and frozen in 10% DMSO/90% autologous plasma in liquid nitrogen. A minimum of 2 doses will be required to proceed with treatment. An aliquot

of the vaccine product will be sent for microbiological assessment consisting of endotoxin, mycoplasma and sterility testing as detailed in the CMC section. Release criteria for vaccine administration are:

- 1) > 50% of DC prep express CD86
- 2) Viability of DC prep > 70%
- 3) Fusion efficiency > 15%
- 4) Fusion viability > 50%
- 5) Sterility, mycoplasma, and endotoxin assays are negative

#### 9.2.4 Administration

Patients will be vaccinated with  $1-5 \times 10^6$  fusion cells in the upper thigh region. The site will be alternated for each vaccine administration (right and left extremity). Vaccination will be administered subcutaneously using a 25-gauge 5/8-inch needle. Tumor vaccine will be administered first, followed by GM-CSF injection.

#### 9.2.5 Ordering

Vaccine will be ordered from the Stem Cell Lab at BIDMC on the day of treatment. The lab should be notified of all scheduled treatment days at least 1 week in advance.

### 9.3 GM-CSF

GM-CSF is commercially available and will be purchased in bulk from commercial supply by the research pharmacy and billed to grant. On the day of vaccination, the clinical research nurse/physician assistant will administer 100 ug of GM-CSF subcutaneously at the site of the vaccine. Research pharmacy will reconstitute the drug with bacteriostatic water at the appropriate dose for the patient. The patient will be trained to inject the remaining three GM-CSF injections (100ug dose once a day) for self-administration subcutaneously at home. Tumor vaccine will be administered first, followed by GM-CSF injection.

## 10. BIOMARKER, CORRELATIVE, AND SPECIAL STUDIES

### 10.1 Correlative Studies

#### 10.1.1 Myeloma-reactive T cells in the peripheral blood

- 10 mLs of peripheral blood will be collected in a green top tube at the pre-immunotherapy visit, prior to cycles 2-6, at each active monthly follow up visit, and at time of progression.
- Specimens will be delivered to the [name] lab at BIDMC.
- Samples will be processed in the [name] lab. Ficoll centrifugation of the peripheral blood sample will be performed to isolate peripheral blood mononuclear cells (PBMCs). PMBCs will be co-cultured with autologous tumor lysate prepared from the enrollment bone marrow aspirate. Surface antibody staining for CD4 and CD8 positive lymphocytes in addition to intracellular staining for IFN gamma will be performed on this co-culture to quantify IFN gamma producing T cells.

#### 10.1.2 Myeloma-reactive T cells in the bone marrow

- 5 mLs of bone marrow aspirate will be collected in a green top tube at the pre-immunotherapy visit, prior to cycle 4, at one, three, and six month active follow up visits and at time of progression.
- Specimens will be delivered to the [name] lab at BIDMC.
- Samples will be processed in the [name] lab. Ficoll centrifugation of the aspirate sample will be performed to isolate bone marrow mononuclear cells (BMMCs). BMMCs will be co-cultured with autologous tumor lysate prepared from the enrollment bone marrow aspirate. Surface antibody staining for CD4 and CD8 lymphocytes in addition to intracellular staining for IFN gamma will be performed on this co-culture to quantify IFN gamma producing T cells.

#### 10.1.3 Effect of treatment on circulating T cells binding the MUC1, NY-ESO, Survivin, PRAME, and WT1 tetramers in HLA-A2.1 patients

- 10 mLs of peripheral blood in a green top tube at the pre-immunotherapy visit, prior to cycles 2-6, at each active monthly follow up visit, and at time of progression.
- Specimens will be delivered to the [name] lab at BIDMC.
- Samples will be processed in the [name] lab using a tetramer assay to isolate tetramer-specific T cells. Functional characteristics of the pentamer positive cells will be determined by quantifying expression of IFN $\gamma$ , granzyme B, IL-4, and IL-10 expression by intracellular FACS staining.

#### 10.1.4 T cell subsets , T cell checkpoint receptors, and MDSCs

- 10 mLs of peripheral blood in a green top tube at the pre-immunotherapy visit, prior to cycles 2-6, at each active monthly follow up visit, and at time of progression.
- 5 mLs of bone marrow aspirate will be collected in a green top tube prior to cycle 4, at one, three, and six month active follow up visits and at time of progression.
- Specimens will be delivered to the [name] lab at BIDMC.
- Samples will be processed in the [name] lab. The PB and BM aspirate samples will undergo ficoll centrifugation to obtain PBMCs/BMMCs. From the PBMCs/BMMCs, T cell subsets and MDSCs will be isolated by antibody staining and quantified by flow cytometric analysis.

#### 10.1.5 Optional vaccine site biopsy

- Patients will be referred to dermatology clinic for a punch biopsy of vaccine site reaction.
- The biopsy specimen will be delivered to the [name] lab at BIDMC.
- Specimens will be stained using immunohistochemistry for T cell, DC, and myeloma markers to assess for immune cell infiltrate and possible tumor infiltrate.

#### 10.1.6 Optional samples for future research studies

- 10 mLs of PB in a green top tube at the pre-immunotherapy visit, prior to cycles 2-6, at each active monthly follow up visit, and at time of progression.
- 5 mLs of bone marrow aspirate will be collected in a green top tube prior to cycle 4, at one, three, and six month active follow up visits and at time of progression.
- These specimens will be delivered to the [name] lab at BIDMC.
- The specimens will be cryopreserved in the [name] lab for possible future research studies.

## 10.2 Sample Collection time points

Sample Collection for Stem Cell Lab	
Required 	At enrollment (at the time of tumor collection)
Bone marrow aspirate for tumor collection (30 mL)	X

Plasma for Vaccine Production (50 mL)	X
Infectious Serologies	X

1. Total tubes: 3 of the 10mL Na-Hep green top tubes aspirate, 5 of the 10mL Na-Hep green top tubes, 2 of the 6mL red top tubes and 3 of the 6mL pink top tubes peripheral blood

Sample Collection for [name] Lab				
Required	At the pre-immunotherapy visit 	Prior to each cycle 	Months 1-6 Active Follow-up 	Disease Progression 
Bone Marrow Aspirate for Myeloma Reactive T Cells (5 mL)	X	X (cycle 4 only)	X (months 1, 3 and 6 only)	X
Bone marrow aspirate for tetramer reactivity (5 mL)	X	X (cycle 4 only)		X
Bone marrow aspirate for T cell subsets, T cell checkpoint receptors, MDSCs (5 mL)		X (cycle 4 only)	X (months 1, 3 and 6 only)	X
Peripheral Blood for Myeloma Reactive T Cells (10 mL)	X	X	X	X
Peripheral blood for tetramer analysis (10 mL)	X	X	X	X
Peripheral blood for T cell subsets, T cell checkpoint receptors, MDSCs (10 mL)	X	X	X	X

1. Total tubes: 3 of the 10mL Na-Hep green top tubes peripheral blood and 2 of the 10mL Na-Hep green top Aspirate  
 2. Total tubes: 3 of the 10mL Na-Hep green top tubes peripheral blood  
 3. These samples do not need to be collection at cycle 1, as they were collected at the pre-immunotherapy visit.

Optional Sample Collection for [name] Lab				
Required	At enrollment (at the time of tumor collection) 	Prior to each cycle 	Months 1-6 Active Follow-up 	Disease Progression 
Optional Peripheral Blood Samples for Future Research (10 mL)	X	X	X	X
Optional Bone Marrow Aspirate Samples for Future Research (5 mL)		X (cycle 4 only)	X (months 1, 3 and 6 only)	X

1. Total tubes: 1 of the 10mL Na-Hep green top tube peripheral blood; 1 of the 10mL Na-Hep green top tube aspirate
2. Total tubes: 1 of the 10mL Na-Hep green top tube peripheral blood

## 11. STUDY CALENDAR

Baseline evaluations are to be conducted within 2 weeks prior to registration.

Assessments must be performed prior to administration of any study agent. Study assessments and agents should be administered within  $\pm$  3 days of the protocol-specified date, unless otherwise noted.

### Cycles 1-3

Study Assessments	Pre-Enrollment	At Enrollment (at the time of tumor collection)	Pre-Immunotherapy	Day 1	Day 15	Day 21
History, physical exam, weight and height	X		X	X	X	
Vital Signs 	X		X	X		
Ambulatory O2 sat 	X		X	X	X	
CBC, differential, platelet count, and blood chemistries	X		X	X	X	
TSH, Free T4, Free T3	X		X	X		
Evaluation of Creatinine Clearance	X		X	X	X	
Pregnancy test	X		X	X		
Quantitative serum immunoglobulins	X		X	X		
SPEP and immunofixation	X		X	X		
24 Hour Urine for UPEP, protein excretion and immunofixation	X		X	X		
Serum free light chain ratio	X		X	X		
B2M, CRP	X		X	X		
Skeletal Survey or alternative imaging	X					
Bone marrow aspirate and biopsy	X		X 			
EKG	X		X	X	X	
Toxicity Assessment	X		X	X	X	
Con Meds	X		X	X	X	
DC/MM Fusion Vaccine and GM-CSF Administration 				X		
Nivolumab Infusion				X	X	
Study Tubes 			X	X		

1. Vitals (BP, HR, Temp, RR, O2 sat) to be taken within 15 minutes prior to start of nivolumab infusion and within 15 minutes following completion.
2. Pulse oximetry should be obtained prior to each dose of nivolumab and at any time a subject has any new or worsening respiratory symptoms. A reading at rest and on exertion should be obtained at each time point. The extent of the exertion should be based on the judgment of the investigator, but should remain consistent for each individual subject throughout the study. If the patient's status changes the investigator can alter the extent of exertion based on their medical judgment. If a subject shows changes on pulse oximetry or other pulmonary-related signs (hypoxia, fever) or symptoms (eg, dyspnea, cough, fever) consistent with possible pulmonary adverse events, the patient should be immediately evaluated to rule out pulmonary toxicity. An algorithm for the management of suspected pulmonary toxicity can be found in Appendix 2 of the IB. Not all results are required to be collected by BMS.
3. GM-CSF will be administered at home by the patient on days 2-4 and recorded on the GM-CSF body chart.
4. Please refer to section 10
5. Skeletal survey/alternative imaging is only needed at the pre-immunotherapy visit if the patient received bridging therapy and this is needed for re-staging.
6. If marrow was done within prior 6 weeks then this does not need to be repeated.

**Cycles 4 - 6**

Study Assessments	Day 1	Day 15
History, physical exam, weight and height	X	X
Vital Signs 	X	X
Ambulatory O2 sat 	X	X
ECOG performance score	X	
CBC, differential, platelet count, and blood chemistries	X	X
TSH, Free T4, Free T3	X	
Evaluation of Creatinine Clearance	X	X
Pregnancy test	X	
Quantitative serum immunoglobulins	X	
SPEP and immunofixation	X	
24 Hour Urine for UPEP, protein excretion and immunofixation	X	
Serum free light chain ratio	X	
B2M, CRP	X	
Skeletal Survey or alternative imaging		
Bone marrow aspirate and biopsy 	X	
EKG	X	X
Toxicity Assessment	X	X
Con Meds	X	X
Nivolumab Infusion	X	X
Study tubes 	X	

1. Vitals (BP, HR, Temp, RR, O2 sat) to be taken within 15 minutes prior to start of nivolumab infusion and within 15 minutes following completion.
2. Pulse oximetry should be obtained prior to each dose of nivolumab and at any time a subject has any new

or worsening respiratory symptoms. A reading at rest and on exertion should be obtained at each time point. The extent of the exertion should be based on the judgment of the investigator, but should remain consistent for each individual subject throughout the study. If the patient's status changes the investigator can alter the extent of exertion based on their medical judgment. If a subject shows changes on pulse oximetry or other pulmonary-related signs (hypoxia, fever) or symptoms (eg, dyspnea, cough, fever) consistent with possible pulmonary adverse events, the patient should be immediately evaluated to rule out pulmonary toxicity. An algorithm for the management of suspected pulmonary toxicity can be found in Appendix 2 of the IB. Not all results are required to be collected by BMS.

3. Please refer to section 10
4. Bone marrow aspirate and biopsy only required on day 1 of cycle 4.

#### Follow Up

Study Assessments	Toxicity Assessment Visit (+/- 7 days) 	Months 1-6 (+/- 7 days)	Progression Free Survival  (+/- 14 days)	Survival Follow-Up (every 6 months for 5 years)
History, physical exam, weight and height	X	X		
Vital Signs 	X	X		
Ambulatory O2 sat 	X	X		
ECOG performance score	X	X		
CBC, differential, platelet count, and blood chemistries	X	X		
TSH, Free T4, Free T3	X	X		
Evaluation of Creatinine Clearance	X	X		
Quantitative serum immunoglobulins		X	X	
SPEP and immunofixation		X	X	
24 Hour Urine for UPEP, protein excretion and immunofixation		X	X 	
Bone Marrow Biopsy and Aspirate	X	X 	X 	
Serum free light chain ratio		X	X	
B2M, CRP		X		
Toxicity Assessment	X	X		
Skeletal Survey or alternative imaging		X 		
Con Meds	X	X		
Survival status	X			X
Study tubes		X 		

0. Only required for patients who are removed from treatment due to progressive disease or to start alternative anti-myeloma therapy per MD discretion
1. Every 3 months after 6 month follow up visit for 5 years
2. Vitals (BP, HR, Temp, RR, O2 sat) to be taken within 15 minutes prior to start of nivolumab infusion and within 15 minutes following completion.
3. A O2 saturation reading at rest and on exertion should be obtained during each study visit.

4. Only required for participants with +UPEP at baseline, otherwise random UPEP is permitted. If the random UPEP is positive, a 24-hour urine collection is required.
5. At Months 1, 3 and 6 follow up and at time of progression.
6. Months 1 and 6 only
7. Please refer to section 10

#### **At Time of Disease Progression**

Study Assessments	At Time of Disease Progression
Quantitative serum immunoglobulins	X
SPEP and immunofixation	X
24 Hour Urine for UPEP, protein excretion and immunofixation 	X
Bone Marrow Biopsy and Aspirate	X
Serum free light chain ratio	X
Study tubes 	X

1. Only required for participants with +UPEP at baseline, otherwise random UPEP is permitted. If the random UPEP is positive, a 24-hour urine collection is required.
2. Please refer to section 10

## **12. MEASUREMENT OF EFFECT**

### **12.1 Definition of Disease Status**

Patients' disease status at each data collection period will be evaluated based on the International Uniform Response Criteria. Until disease progression, all disease classifications are relative to the patient's disease status prior to autologous transplant (i.e. study entry). At time of disease progression, disease classifications are relative to the patient's best response since time of study entry.

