## **1. OBJECTIVES**

### **1.1 Study Design**

The study is a phase II study to evaluate vaccination with DC/myeloma fusions/GM-CSF and nivolumab in patients diagnosed with relapsed multiple myeloma previously treated with a proteasome inhibitor, IMiD, and anti-CD38 mAb therapy. Patients meeting initial eligibility will be enrolled and vaccine production will be initiated via the harvesting of autologous tumor cells and generation of DCs from adherent mononuclear cells. During the period of vaccine generation, patients will undergo therapy with 1-2 cycles of standard of care therapy. Patients without disease progression will then undergo monthly vaccination with DC/MM fusions for cycles 1, 2, and 3 in conjunction with nivolumab administered on day 1 and 15 and will then receive nivolumab alone for 3 additional cycles, for a total of 6 cycles of treatment.

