3.2.3 Participants with Plasma Cell Leukemia

3.2.4 Because of compromised cellular immunity, patients who have a known human immunodeficiency virus (HIV), active hepatitis C virus (HCV) or active hepatitis B virus (HBV).

3.2.5 Myocardial infarction within 6 months prior to enrollment or New York Heart Association (NYHA) Class III or IV heart failure (see Appendix H), uncontrolled angina, severe uncontrolled ventricular arrhythmias, or electrocardiographic evidence of acute ischemia or active conduction system abnormalities. Prior to study entry, any ECG abnormality at screening will be documented by the investigator as not medically relevant.

3.2.6 Active or prior documented autoimmune or inflammatory disorders including but not limited to the following:

- GI Disorders: (including inflammatory bowel disease [e.g. ulcerative colitis, Crohn's disease], diverticulitis (with the exception of a prior episode that has resolved), celiac disease, or other serious gastrointestinal chronic conditions associated with diarrhea.
- Systemic lupus erythematosus
- Wegener's syndrome [granulomatosis with polyangiitis]
- Myasthenia gravis
- Graves' disease
- Rheumatoid arthritis
- Hypophysitis
- Uveitis

The following are exceptions to this criterion: subjects with vitiligo or alopecia; subjects with hypothyroidism (e.g. following Hashimoto syndrome) stable on hormone replacement; or subjects with psoriasis not requiring systemic treatment.

3.2.7 Individuals with a history of a different malignancy are ineligible except for the following circumstances. Note: Individuals with a history of other malignancies are eligible if they have been disease-free for at least 5 years and are deemed by the investigator to be at low risk for recurrence of that malignancy. Individuals with the following cancers are eligible if diagnosed and treated within the past 5 years: non-invasive cancer (such as, any *in situ* cancers) and basal cell or squamous cell carcinoma of the skin.

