## **5. TREATMENT PLAN**

On this study, patients will be enrolled and undergo tumor collection and dendritic cell collection per protocol. Patients will undergo 1-2 cycles of standard of care therapy during the period of vaccine preparation. Patients for whom vaccine production is successful will undergo vaccination with DC/MM fusions on day 1 of cycle 1, 2, and 3. Subsequent cycles (following cycle 3) will consist of Nivolumab alone on Days 1 and 15 for a total of 6 cycles.

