### **5.1 Evaluations Prior to Enrollment**

The following evaluations must be performed within 2 weeks prior enrollment

1. History, physical examination, height and weight
2. ECOG Performance Status
3. Baseline AE Evaluation
4. CBC with differential
5. Liver Functions and blood chemistries: Na, K, Cl, CO2, Ca, Mg, PO4, Creatinine, total bilirubin, direct bilirubin, alkaline phosphatase, AST, ALT, LDH
6. Beta-2 Microglobulin, CRP
7. TSH, Free T4, Free T3
8. Evaluation of creatinine clearance
9. Pregnancy test in FOCBP
10. Laboratory Disease Evaluation:
  - Quantitative serum immunoglobulin levels.
  - Serum protein electrophoresis (SPEP).
  - 24-hour urine collection to determine creatinine clearance and protein excretion, urine electrophoresis (UPEP).
  - Immunofixation of urine and serum protein regardless of SPEP and UPEP results.
  - Serum free light chain ratios (FLC)
11. Bone marrow to assess plasma cell involvement in the marrow as per eligibility criteria. Unilateral bone marrow biopsy and aspirate are required. If performed within 30 days it does not need to be repeated.
12. Skeletal bone survey to include cranium, axial skeleton and proximal long bones or alternative imaging to capture areas of bone disease

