## **5.3 Dendritic Cell Collection**

Patients may receive up to 1 cycle of bridging therapy prior to undergoing leukapheresis. Leukapheresis will be performed when after recovery of blood counts (an ANC >1000 K/uL and PLT >50 K/uL). When possible, leukapheresis will be performed via peripheral access. If peripheral access is inadequate, patients will undergo placement of a temporary central venous catheter. Standard infectious serologies will be drawn within 8 days of isolation dendritic cells as per BIDMC practice for storage of cellular products (drawn in 2 red top tubes and 3 pink top tubes and sent to the Stem Cell Lab at BIDMC).

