## **5.4 SOC Anti-Myeloma Bridging Therapy During Period of Vaccine Preparation**

Patients may receive up to 2 cycles of standard of care therapy following leukapheresis. Bridging therapy is at the discretion of the physician, however the use of IMiDs (ie. Lenalidomide or pomalidomide) is prohibited.

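### Section 12.1 leaves the response baseline undefined and most likely sets it before bridging therapy, so a partial response won on bridging can count in the secondary ORR test

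*Combined protocol and SAP*

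**What the plan says.** **Baseline.** Until progression, section 12.1 makes every classification relative to "disease status prior to autologous transplant (i.e. study entry"). At progression, the reference becomes the best response since study entry. Section 12.2.7 measures progression outside CR from randomization.

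**Study entry.** The term is not defined. Section 11 says: "Baseline evaluations are to be conducted within 2 weeks prior to registration". Section 5.1 sets the same two-week window before enrollment. Exclusion 3.2.5 links the term to screening: "Prior to study entry, any ECG abnormality at screening will be documented by the investigator".

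**Between enrollment and cycle 1.** Section 1.1 says: "During the period of vaccine generation, patients will undergo therapy with 1-2 cycles of standard of care therapy". Section 5.3 says: "Patients may receive up to 1 cycle of bridging therapy prior to undergoing leukapheresis". Section 5.4 says: "Patients may receive up to 2 cycles of standard of care therapy following leukapheresis".

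**Before immunotherapy.** Section 3.3 has several conditions (toxicity, vaccine yield, ECOG, organ function, washout). The only one based on disease response is that the patient has not progressed. Section 5.5 requires restaging and a second registration, but does not call that visit the baseline for response.

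**Use.** Section 1.3.2 asks about the clinical response to nivolumab and the vaccine. Section 14.1 tests ORR by a one-sided 10% exact binomial test, 0.15 versus 0.35, n = 25, stated power 82%, and treats 35% as enough to justify a larger trial.

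**The concern.** Bridging lies between the likely baseline and the first dose of study treatment. A patient whose paraprotein halves on bridging and then stays flat would meet the serum part of PR without any effect of nivolumab or vaccine. Patients in a bridging response proceed to treatment, since only progressors are removed. The ORR, which informs the decision on a larger trial, could then mix the effect of bridging drugs with that of the study treatment.

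The error can also run the other way. Paraprotein that rises on bridging, short of progression, raises the level from which a later fall starts. Measured from the lower enrollment value, a real response may not reach 50%.

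**Working it through.** **1. Which visit the text points to.** The transplant does not occur, so study entry is the only usable anchor. Sections 5.1 and 11 place the baseline evaluations before enrollment or registration, and 3.2.5 places study entry close to screening. Sections 1.1, 5, 5.3 and 5.4 place bridging after enrollment. The rival reading is the second registration in section 5.5, but nothing links it to response. Enrollment is the likelier reading; the text does not settle it.

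**2. Both errors in single patients** (illustrative serum values in g/dL, urine criterion taken as met).
- Upward: 4.0 at enrollment, 1.8 after bridging, 1.8 on study. Fall from enrollment (4.0 − 1.8)/4.0 = 55%, so PR. Fall from the pre-immunotherapy value 0%.
- Downward: 2.0, then 2.4, then 1.15. The rise on bridging is 20% and 0.4 g/dL, below both limits in 12.2.7. Fall from enrollment (2.0 − 1.15)/2.0 = 42.5%, not PR. Fall from the pre-immunotherapy value (2.4 − 1.15)/2.4 = 52.1%, which meets the serum threshold.

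**3. The plan's own figure.** With X ~ Bin(25, p), P(X ≥ 6 | 0.15) = 0.1615 exceeds 0.10 and P(X ≥ 7 | 0.15) = 0.0695 does not. The implied rule is 7 or more of 25. Power is P(X ≥ 7 | 0.35) = 0.8266, which agrees with the stated 82%.

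**4. Fixed number of carry-over PRs.** Let t be the true ORR against the pre-immunotherapy baseline and k the number of patients counted only because of a persisting bridging PR. Then P(success) = P(Y ≥ 7 − k), with Y ~ Bin(25 − k, t). Both k and t are assumptions.

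| True ORR t | k = 0 | k = 1 | k = 2 | k = 3 |
|---|---|---|---|---|
| 15% | 0.070 | 0.139 | 0.256 | 0.425 |
| 10% | 0.010 | 0.028 | 0.073 | 0.172 |
| 5% | 0.0002 | 0.001 | 0.005 | 0.022 |

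**5. Random share, a separate model.** Let each patient have an assumed probability b of a persisting bridging PR, so the apparent ORR is p = b + (1 − b)t. P(X ≥ 7) reaches 0.10 at p = 0.1632, so b = (0.1632 − t)/(1 − t).

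| True ORR t | b | Expected carriers, 25b |
|---|---|---|
| 15% | 1.5% | 0.4 |
| 10% | 7.0% | 1.8 |
| 5% | 11.9% | 3.0 |
| 0 | 16.3% | 4.1 |

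The two models are not conversions of each other. At t = 5%, b = 11.9% (3.0 carriers expected) gives 0.10, while exactly three carriers give 0.022, because in the random model the number of carriers also varies.

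**6. Allowing for missed responders.** Let m be the share of true responders missed, at t = 15%.
- If only non-carriers can be missed, p = b + (1 − b)t(1 − m). The bias cancels at m = 30% for b = 5% and at 63% for b = 10%.
- If any true responder can be missed, p = t(1 − m) + (1 − t)b. It cancels at 28% and 57%.

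With b = 5% and m = 20%, P(success) is 0.102 in the first and 0.098 in the second, on either side of 0.10.

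**The case against.** Section 12.1 does supply an anchor: the parenthesis names study entry, and the next sentence uses that term without the transplant. The transplant words are probably left over from another protocol. This stands. The defect is an undefined and probably unsuitable baseline, not the absence of one. The ECG criterion is also limited support, since it puts study entry after screening rather than at it, and section 5.5 has a second registration.

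Bridging responses may be uncommon. Patients have had at least three prior lines and have relapsed after, or are refractory to, three drug classes (3.1). IMiDs are barred from bridging (5.4), and myeloma therapy other than steroids stops seven days before treatment (3.3.6). The documents report no response to vaccine alone in relapsed disease (14.1) and minimal single-agent PD-1 activity (2.6), so a true ORR well below 15% is plausible. There, one to three carriers hardly matter. This stands too, as a limit on size.

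A reader might infer that the ORR is biased upward, or that its test is invalid. The documents do not support that. Removing progressors cuts off rises on bridging but not falls, which makes a net upward bias plausible. No rate is given for bridging responses or for rises short of progression, and step 6 shows that the balance depends on the assumed shares and on the model.

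**Conclusion.** The point holds as a defect in the definition of the response baseline, and it should be fixed. On the likelier reading of study entry, the ORR rule can credit bridging responses to nivolumab plus vaccine, and it can also hide some true responses. Net bias is plausibly upward; its direction and size cannot be established.

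The probabilities above are illustrations under assumed carry-over. The large ones (0.139 to 0.425) arise only at a true ORR of 15%. At 5%, three carriers leave P(success) at 0.022.

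The effect is confined to the secondary clinical endpoint. A reader might infer that the primary immune endpoint shares the problem. It does not, because section 10.1.1 takes its baseline sample at the pre-immunotherapy visit.

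**What to change.** 1. In 12.1, delete the transplant wording and define the ORR baseline as the last disease evaluation before the first dose of study treatment. Name one visit: section 5.5, or the cycle 1 day 1 laboratory tests if drawn before dosing.
2. Report ORR against the enrollment value as a sensitivity analysis.
3. In 12.2.7, replace the reference to randomization with one consistent with 12.1.
4. State in advance how patients without measurable disease at the chosen baseline, or without marrow or imaging after bridging, are handled in the ORR.

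**Cost.** No new serum, urine or light-chain tests are needed; sections 5.5 and 5.6 already schedule them. Marrow may be omitted if done within six weeks, and imaging at that visit is conditional, so some patients will lack these after bridging. Few should depend on marrow alone, since purely non-secretory disease is excluded (3.2.2).

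The real cost is power. Suppose 2 or 3 of 25 have no measurable disease and stay in as non-responders, and the others respond at 35%. Power falls from 0.83 to P(X ≥ 7 | 23, 0.35) = 0.75 or P(X ≥ 7 | 22, 0.35) = 0.70.

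**Separately,** sections 1.1, 5, 5.3 and 5.4 (standard-of-care therapy, with differently worded cycle limits) and section 14.1 (an initial cycle of nivolumab) must be reconciled on what is given during vaccine production. Until they are, it is not certain which visit precedes the first dose. This contradiction is not evidence for bias in the ORR.
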